j For women of child-bearing potential only, a qualitative serum pregnancy test will be performed at screening and an on-site urine test performed at baseline; Weeks 4, 8, 12, 24, 36, 48, and 52; the ET visit and the safety follow-up visit. When there is no site visit, the patients will perform urine pregnancy tests themselves at home, ie, at Weeks 16, 20, 28, 32, 40, and 44.

k RF and ACPA will only be collected at screening.

- l Blood samples for human immunodeficiency virus, hepatitis B virus, and hepatitis C virus will be obtained at screening.
- m The tuberculosis Quantiferon-Gold test will only be performed in patients whose previous test was negative. Continuation of study medication will be excluded in patients who were QFT negative at randomization, but subsequently become QFT positive at Week 24.
- n If a bi-directional X-ray is available from the last 3 months before planned randomization, the exam will not be repeated at screening.
- o The ECG will be repeated at the ET or 4-week/4-month Safety/Follow-up visit only if in the opinion of the Investigator it is clinically warranted.
- p Patient reported outcome questionnaires and the Physician's Global Assessment of Disease Activity must be performed prior to any other assessments at all visits.
- q Performed locally.
- r All blood samples for immunogenicity assessment and IMP concentration must be drawn prior to administration of the IMP, which will be performed at the site for these visits. The date and exact time of sample collection must be recorded.
- s For assay validation purposes only, no result(s) will be reported.
- t Injection site pain (VAS) immediately post-injection, 15 min post-injection, and 1 hour post-injection. If the pain has not resolved by 1 hour post-injection, the patients will be asked to record when the pain resolves. Injection site pain during 3rd, 4th, and 5th injection will be reported as adverse event similar to any injection site reactions at other time point of IMP administration. The first 2 injections will be administered by qualified personnel. The next three doses of IMP (3-5) will be self-administered by the patient and injection site pain will be assessed. Pain will be recorded immediately after, 15 minutes after, and 1 hour after the injections received by the patient.
- u Injection site pain will be recorded by the patient at home.

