Patients will be evaluated for latent TB infection (LTBI) by the QFT enzyme-linked immunosorbent assay and by chest X-ray. If a patient tests positive for LTBI at screening, the patient will be screen failed and will not be randomized. Patients with indeterminate QFT test result may be re-tested once within the screening period:

- i. If the re-test is negative, the patient is eligible to take part in the trial.
- ii. If the re-test is positive, the patient will not be eligible to participate in the trial.
- iii. If the re-test is again indeterminate, the patient will be considered as having LTBI and will not be eligible to participate in the trial. No further QFT will be performed.
12. Received a live vaccine within 3 months prior to IMP administration or intends to receive a live vaccination during the trial or within 3 months after the last dose of IMP.
13. History of hypersensitivity to any component of the IMP formulation, comparable drugs, or latex.
14. Any infection as follows:
  - a. Requires treatment with oral antibiotics within 14 days prior to IMP administration.
  - b. A serious infection defined as requiring hospitalization or treatment with intravenous antibiotics within 8 weeks prior to IMP administration.

- c. Has had herpes zoster or any opportunistic infection (eg, histoplasmosis, coccidioidomycosis, blastomycosis, pneumocystis, listeriosis, legionellosis, or parasitic infections) within 6 months prior to administration of IMP.
- d. A history of persistent chronic infection or recurrent infections (3 or more of the same type of infection in any rolling 12 month period, eg, urinary tract or upper respiratory tract infections).
- e. Have documentation of seropositivity for human immunodeficiency virus (HIV), or positive hepatitis C antibody test or hepatitis B surface antigen test and/or core antibody test for IgG and/or IgM or total Ig at screening.

15. History of lymphoproliferative disease or previous malignancy. Curatively treated basal or squamous cell carcinoma of the skin is not excluded, unless it occurred within 12 months of randomization. Curatively treated localized in situ carcinoma of the cervix is also not excluded, if there is no evidence of recurrence within the last 5 years prior to randomization.

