##### **6.4.3.1 Management of Latent Tuberculosis Infection Diagnosed During the Study**

It is highly recommended to adhere to national/institutional guidelines to manage and treat subjects diagnosed as LTBI during the study.

Patients with a positive QFT at screening will be ineligible for the trial. Investigators may treat them per local/national guidance for LTBI outside of the study.

If a patient with a negative QFT during screening develops a positive QFT during the trial (ie, at Week 24), treatment with IMP should be stopped and an early termination visit completed. Such patients continue safety/immunogenicity visits (see [Table 1](#) for schedule of assessments). The patient will return for a safety follow-up visit 4 weeks after the last dose of IMP and an additional safety evaluation visit 4 months after the last dose of IMP.

During this 4-week safety follow-up period no excluded treatment for RA (as defined in the protocol) should be administered. Patients will return for an additional safety follow-up visit 4 months after the last dose of IMP. Treatment for RA from the 4-week safety follow-up visit to the 4-month visit will be at the discretion of the Investigator following institutional standard of care. The 4-week and 4-month safety follow-up visits will not be duplicated if either of these visits falls within 2 weeks of an otherwise scheduled visit. If the 4-week and 4-month safety follow-up visits since the last IMP are completed within the 52-week visit schedule, these will not be repeated thereafter.

Patients who were QFT-negative at randomization but subsequently become QFT-positive at Week 24 should, at the safety follow-up visit (4 weeks after the last IMP administration), be referred by the Investigator for a consultation with an infectious disease specialist/pulmonologist as necessary in order to assess whether TB re-activation occurred during the trial.

Patients who were QFT-negative at randomization and at Week 24 but subsequently became QFT-positive at Week 52 should be referred by the Investigator for a consultation with an

infectious disease specialist/pulmonologist as necessary in order to assess whether TB re-activation occurred during the trial.

If a patient develops active TB disease during the trial, treatment with IMP should be stopped immediately.

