### 7.2.3.2 **QuantiFERON-TB Gold In-Tube assay**

A QFT will be performed to assess the TB status during screening for all patients. Additional tests will be performed according to the Schedule of Assessments for patients whose previous QFT was negative. The QFT test will be supplied and analyzed by the central laboratory. Details on the collection, shipment of samples and reporting of results by the central laboratory are provided in the Laboratory Manual. Refer to Section [6.4.3.1](#) for guidance on treatment for patients with TB.

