16.5.2 Tuberculosis Assessments

After initial TB assessments are carried out at screening, QuantiFERON-TB Gold tests are carried out at Weeks 24 and Week 52 during the study.

Completion status (done/not done) and result (negative/positive) will be summarized by visit and treatment arm.

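### An indeterminate on-study QFT result has no stated path, and the previous-negative condition removes that patient from the scheduled Week 52 or early termination test

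*Protocol*

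**What the plan says.** **On-study testing.** Table 1 schedules QFT at screening, Week 24, Week 52 and the early termination (ET) visit. Footnote m limits it: "The tuberculosis Quantiferon-Gold test will only be performed in patients whose previous test was negative". Protocol 7.2.3.2 has the same limit: "Additional tests will be performed according to the Schedule of Assessments for patients whose previous QFT was negative".

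**Consequences on study.** Footnote m: "Continuation of study medication will be excluded in patients who were QFT negative at randomization, but subsequently become QFT positive at Week 24". Section 6.4.3.1 agrees: if a patient who was negative at screening "develops a positive QFT during the trial (ie, at Week 24), treatment with IMP should be stopped". Referral to a specialist also needs a positive result (footnote v and 6.4.3.1). The Week 52 referral in 6.4.3.1 further assumes a negative Week 24 test: "Patients who were QFT-negative at randomization and at Week 24 but subsequently became QFT-positive at Week 52 should be referred".

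**Indeterminate results.** These appear only in exclusion criterion 11 (Protocol 5.3.2), for screening: "Patients with indeterminate QFT test result may be re-tested once within the screening period". The rule then goes on: "If the re-test is again indeterminate, the patient will be considered as having LTBI and will not be eligible to participate in the trial".

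**Withdrawal.** Protocol 5.4.1 lists development of active or latent TB as a reason to end study drug. It also lists a clinically relevant exclusion criterion that arises on study, where the Investigator or Sponsor considers stopping necessary. Neither item mentions an indeterminate QFT.

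**Analysis.** SAP 16.5.2 states that QFT is carried out at Weeks 24 and 52, without the previous-negative condition. It plans: "Completion status (done/not done) and result (negative/positive) will be summarized by visit and treatment arm".

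**The concern.** The protocol knows that QFT can be indeterminate and has a rule for it at screening, but that rule stops at randomization. On study the condition for testing is a previous negative, and an indeterminate result is not a negative. The wording therefore does more than leave a gap. It takes a patient whose status has become unknown out of a test that is already in the schedule.

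Protocol 3.3 names TB reactivation as a known risk of adalimumab, and the primary objective is safety up to Week 52. About 50 sites would each have to decide what to do with such a result. In the output, a completed indeterminate test has no result category at Week 24, and at Week 52 the patient would look the same as one whose test was simply missed.

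**Working it through.** The plan gives no figure to reproduce. The check follows each possible Week 24 outcome through every QFT rule. Under criterion 11 a patient enters with a negative QFT: a positive is excluded, and a re-tested indeterminate must turn negative. The condition is therefore met for everyone going into Week 24.

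| Week 24 outcome | Study drug | QFT at Week 52 or ET | Referral | SAP 16.5.2 |
|---|---|---|---|---|
| Negative | Continues | Done | If later positive | Done, negative |
| Positive | Stopped (footnote m, 6.4.3.1) | Not repeated | Yes | Done, positive |
| Test missed | No QFT result to act on | Done, because the last test is the negative one at screening | Footnote v, if positive | Not done |
| Indeterminate | No QFT-based rule | Not done, because the previous test was not negative | None stated | Done, but neither result |

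Four things follow.

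1. *Missed versus indeterminate.* A patient who misses Week 24 is tested at Week 52; a patient who attends and has an indeterminate result is not. It is hard to see this as intended.
2. *Screening versus on study.* At screening, one indeterminate leads to a possible re-test and two count as latent TB. On study, the testing condition blocks the later scheduled test that could supply a second result, and no other re-test is described. Whether an on-study indeterminate can ever count as latent TB under 5.4.1 cannot be settled from the text.
3. *Exposure.* Doses are every 2 weeks and the last is at Week 48. After Week 24 that leaves (48 − 26)/2 + 1 = 12 doses at most. A patient may also stop earlier, for example under the joint-count rule.
4. *Tabulation.* Let T be the patients tested, made up of N negative, P positive and I indeterminate, so T = N + P + I. SAP 11.1 bases percentages on non-missing data but does not say how an indeterminate is coded. If it is missing, the denominator is N + P. If it is non-missing, the denominator is T and the two printed percentages add up to 100 × (1 − I/T), with no row for the rest.

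The documents give no value for I/T, so no number of patients can be computed.

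**The case against.** The strongest reply is that footnote m is shorthand for not re-testing known positives. The footnote also hangs on the row label, where a literal reading would bar the first test at screening, and 7.2.3.2 plainly requires that test for all patients. The point has some weight. But 7.2.3.2 separately states the same condition for the additional tests, so the limit does not rest on a loosely placed footnote. That section also refers to a Laboratory Manual for collection, shipment and reporting. The manual is not available here and may cover repeat samples, but it should not have to override an explicit protocol limit.

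Three stronger readings are tempting, and the documents do not support them.

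- *That the patient must stay on drug.* The text only lacks a rule that requires stopping. Protocol 5.4.1 leaves a discretionary route, and sections 6.3 and 6.7 have the site confirm that the patient may remain in the trial before kits are assigned.
- *That TB surveillance ends at Week 24.* Only the scheduled QFT lapses. Physical examination continues at Weeks 36, 48 and 52, adverse events are reviewed at each visit, active TB stops study drug at once (6.4.3.1), and the IDMC reviews safety throughout.
- *That a conversion rate by arm is biased.* The SAP plans no conversion rate. It plans counts by visit and arm, and QFT is not among the listed endpoints. Loss of indeterminates from the denominator is possible but not stated, and all data are also listed by subject (SAP 11.3).

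**Conclusion.** The point holds as an inconsistency between the screening rule and the on-study rules. Read literally, footnote m and 7.2.3.2 remove a patient with an indeterminate Week 24 result from the scheduled Week 52 or ET test. No stated rule covers re-test, stopping or referral for that patient. This sits badly with criterion 11 and with the latent-TB item in 5.4.1.

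Its size is unknown: the number affected depends on an indeterminate rate that the documents do not give, and it may be small or zero. For any such patient the gap is up to 12 doses without a further scheduled QFT. The primary endpoint, the key secondary endpoint and the sample size are untouched. It should still be corrected, because it concerns a known risk of the drug class in a trial whose primary objective is safety, and the correction is cheap. The conclusion assumes that the condition is applied as written and that no document outside the protocol and SAP sets a different rule.

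**What to change.** **Protocol.** Reconcile footnote m, 7.2.3.2, 6.4.3.1 and 5.4.1 with exclusion criterion 11 on two matters:

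- The previous-negative condition should not by default remove patients of unknown status from the scheduled Week 52 or ET test.
- An on-study indeterminate result should have one stated path. The clinical team sets that path; this review does not propose one.

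**SAP 16.5.2.** Add indeterminate as a result category beside negative and positive, with all tested patients at the visit as denominator. State the testing condition in force, so that a Week 52 test not done by rule can be told apart from one that was missed.

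**Cost.** A protocol clarification, one extra table category, and possibly a few more QFT samples, depending on the path chosen.

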## 2 Sponsor, Investigators and Trial Administrative Structure

The Sponsor of this clinical trial with MSB11022 is EMD Serono Research & Development Institute, Inc. (EMD Serono R&D), Billerica, MA, in the United States of America (USA) and Merck KGaA, Darmstadt, Germany, in rest of world.

The trial will be conducted at approximately 50 sites in 6 countries in Europe.

The Coordinating Investigator represents all Investigators for decisions and discussions regarding this trial, consistent with the International Council for Harmonisation (ICH) Topic E6 Good Clinical Practice (GCP; hereafter referred to as ICH GCP). The Coordinating Investigator will provide expert medical input and advice relating to trial design and execution and is responsible for the review and signoff of the clinical trial report.

Signature pages for the Protocol Lead and the Coordinating Investigator as well as a list of Sponsor responsible persons are in [Appendix B](#).

The trial will appear in the following clinical trial registries: Clinicaltrials.gov, EU clinical trial registry and national registries as per local regulations.

A contract research organization (CRO), PPD, will undertake the operational aspects of this trial with oversight by the Sponsor. Details of such structures and associated procedures will be defined in a separate Integrated Project Management Plan (IPMP). The IPMP will be prepared by the PPD Clinical Project Manager in cooperation with other PPD Operational Team Leads. Clinical quality assurance will be performed under the responsibility of the Development Quality Assurance department at Merck KGaA Darmstadt.

An Independent Data Monitoring Committee (IDMC) will be established to continually review available safety and tolerability data. The IDMC will be composed of independent physicians and an independent biostatistician. The full list of IDMC members and IDMC responsibilities will be included in the IDMC charter.

The investigational medicinal products (IMP) will be supplied by the Clinical Trial Supply Department of the Sponsor and packaged and labeled by PPD.

Details of structures and associated procedures will be defined in a separate Manual of Operations, which will be prepared under the supervision of the Clinical Trial Leader.

## 3 Background Information

### 3.1 Adalimumab

Adalimumab is a tumor necrosis factor (TNF) inhibitor indicated in the European Union (EU) and United States (US) for the treatment of multiple medical conditions, including rheumatoid arthritis (RA), polyarticular juvenile idiopathic arthritis (JIA), enthesitis-related JIA (EU only), psoriatic arthritis, ankylosing spondylitis, axial spondyloarthritis (EU only), Crohn's disease, ulcerative

colitis, plaque psoriasis, pediatric plaque psoriasis (EU only), pediatric Crohn's disease, hidradenitis suppurativa, and uveitis. It is a recombinant human monoclonal antibody expressed in Chinese Hamster Ovary cells which binds specifically to TNF and neutralizes the biological function of TNF by blocking its interaction with the cell surface TNF receptors, p55 and p75.

MSB11022 is a proposed biosimilar of adalimumab (Humira®). To establish biosimilarity per international regulations, the biological product must be highly similar to the reference product notwithstanding minor differences in clinically inactive components and there must be no clinically meaningful differences between the biological product and the reference product in terms of the safety, purity, and potency of the product (1). Development of a biosimilar generally includes a comparison of the proposed product and the reference product with respect to structure, function, human pharmacokinetics (PK) and pharmacodynamics (PD), clinical immunogenicity and clinical safety and effectiveness. If a product meets the requirements of biosimilarity and upon scientific justification, the potential exists for the proposed product to be approved for additional indications of use for which the reference product is approved. (2, 3, 4).

MSB11022 has previously undergone extensive analytical characterization compared to the reference product. In a recently conducted Phase I study, EMR200588-001, a citrate-based formulation (MSB11022-citrate) that showed a high degree of similarity has demonstrated PK similarity to the EU-approved and US-licensed reference products in healthy volunteers. In that study, the 90% confidence intervals (CIs) of the geometric least squares (LS) mean ratios (MSB11022-citrate/US-licensed Humira, MSB11022-citrate/EU-approved Humira®, and US-licensed Humira®/EU-approved Humira®) for area under the plasma concentration time curve from zero to the last measurable time point (AUC[0-last]), area under the plasma concentration time curve from zero to infinity (AUC[0-inf]), and maximum plasma concentration (Cmax) were all entirely contained within the predefined equivalence interval of 80.00% to 125.00%. Therefore, MSB11022-citrate showed an equivalent PK profile to the 2 reference treatments, US-licensed Humira® and EU-approved Humira®; and US-licensed Humira® showed an equivalent PK profile to EU-approved Humira®, following a single subcutaneous (s.c.) injection administration of 40 mg. The safety and immunogenicity data supported the clinical similarity of MSB11022 to both US-licensed Humira® and also EU-approved Humira®.

EMR200588-002, a pivotal Phase III study designed to demonstrate equivalent efficacy of MSB11022-citrate versus EU-approved Humira® is currently ongoing in patients with moderate to severe chronic plaque psoriasis. Studies EMR200588-001 and EMR200588-002 will together constitute the core package for dossier submission for marketing authorization for the citrate-based formulation of MSB11022.

For potential commercialization, a new (CC1 [REDACTED] based) formulation has been developed. A thorough compatibility exercise has been performed between the two MSB11022 formulations, MSB11022-citrate and MSB11022-CC1 [REDACTED]. Results from extensive characterization of the drug substance and product batches showed comparable characteristics. Therefore the product used in the Phase I EMR200588-001 and Phase III EMR200588-002 clinical trials is representative of the product, MSB11022-CC1 [REDACTED] to be used in the proposed Phase III MS200588-004 clinical trial. The planned MS200588-0004 study will use this new CC1 [REDACTED] formulation and will offer supportive

evidence by providing safety, immunogenicity, and efficacy data in a major approved indication for adalimumab, RA.

Refer to the Investigator's Brochure (IB) for further information about the nonclinical and clinical programs and guidance for the Investigator.

This clinical trial will be conducted in compliance with the clinical trial protocol, ICH GCP, and any additional applicable regulatory requirements.

Based on the available quality, nonclinical and clinical data to date, the conduct of the trial specified in this protocol is considered justified (see Section 5.2.1).

### 3.2 Rheumatoid Arthritis

Rheumatoid arthritis is a chronic autoimmune disorder affecting about 1% of the adult population worldwide (5). It is characterized by chronic inflammation of the synovial joints, particularly the small joints of hands and feet, which often leads to destruction of articular cartilage and juxta-articular bone. Most patients have a progressive course that eventually leads to considerable functional disability. A wide array of factors including geographical location, age, gender, infection, oxidative stress and genetic predisposition are known to be involved in the list of causative agents of RA (6, 7).

Juvenile idiopathic arthritis affects individuals up to 16 years of age, and often persists throughout adult life; both the systemic (sJIA) and the poly-articular (pJIA) forms of the JIA may be considered as the pediatric counterparts of the adult forms of RA. The destructive potential of both RA and JIA can be observed even in the earliest stage of the disease. While joints constitute the main target of the anatomical damage, both RA and JIA are systemic conditions and they are often accompanied by extra-articular manifestations such as fever, anemia, fatigue, and osteoporosis. The pathogenesis of these diseases is complex and involves both humoral and cellular reactions including immune-complex formation, vascular reactions and infiltration of lymphocytes and monocytes into the synovium. These infiltrating cells and synoviocytes release pro-inflammatory cytokines that perpetuate inflammation and destruction through effects on other cell types in the synovium and periarticular structures (8).

Reactive oxygen and nitrogen species have been shown to cause tissue injury and pathophysiological consequences in chronic inflammatory conditions such as RA and other rheumatic diseases (9). The basic pathology in the synovium of RA is hyperplasia, increased vascularity and inflammatory cell infiltration. The principal cells among the infiltrates are activated CD4+ T-cells which produce cytokines such as IL-1, IL-6 and TNF- $\alpha$ . TNF- $\alpha$  is a potent cytokine involved in normal inflammatory and immune response. Individuals with RA have high levels of TNF- $\alpha$  in the synovial fluid and it plays an important role in inflammation and joint destruction that are hallmarks of RA. Anti-TNF- $\alpha$  therapy induces a shift in the cytokine equilibrium producing more anti-inflammatory cytokines. Studies have demonstrated dramatic improvement in synovial inflammation in RA patients after treatment with neutralizing anti-TNF- $\alpha$  Abs or soluble TNF receptors, and decreased joint destruction after treatment with IL-1Ra. Immunosuppressive and anti-inflammatory cytokines, including TGF $\beta$ , IL-10 and IL-1Ra are highly and consistently expressed during RA synovitis. Production of these cytokines has been

proposed to reflect the patient's attempts to contain or control inflammation and achieve homeostasis (10).

In particular, IL-6 is a pleiotropic cytokine playing a pivotal role in the pathogenesis of both RA and JIA (11). For example its role for the process of B-cell maturation and the consequent production of auto-antibodies has been demonstrated. It also directly triggers the production of C-reactive protein (CRP) from hepatocytes. In animal models of autoimmune diseases, IL-6 also plays a critical role in the generation of Th17 pro-inflammatory lymphocytes. In patients with established RA, many of the articular and systemic manifestations could be explained by the biologic effect of IL-6 (8).

